7. STATISTICAL ANALYSES

7.1. Exploratory Analyses

7.1.1. Overview of Planned Exploratory Analyses

The efficacy analyses will be based on the “Full Analysis Set” population, unless otherwise specified.

Data Quality Deviators (for data points at each protocol time point):

Activity & Night time Rest endpoints

For all the actigraphy endpoints if the difference between visits of ALSFRS and Actigraphy is more than 21 days then the data will be excluded and will not be used for the summaries. If the first time point within a visit falls within the 21 days window, then all the time points will be considered.

Using the default sleep times for this study (22:00-07:00) which are derived from the day and night anchor times (set by the day/night algorithms used in this study), the amount of data present for a 24-hour recording period was calculated by adding up the durations for activity classifiers: active + sedentary [where sedentary = sedentary not lying + lying]. If the amount of data present is too low (conversely the amount of “off” time is too high) then the data will not be representative of a full day or night, because a subject’s pattern of activity throughout a day or night is not expected to be homogenous or uniform.

A review of the literature showed that a variety of rules can be used, ex. for daytime recordings: 70-75% of data present, 10 of 16 hours (63%) data present. There are not set rules or standards. As this study utilises 22 hours recording (2 hours permitted for charging), the study team decided on the following limits: 70% for the day and 60% for the night. The % is set lower for the night as it was recognised that subjects may have more problems with night (either due to their disease, or with the technology) and so the amount of valid usable data for a night might be expected to be less. [Tudor-Locke, 2012]

Daytime Endpoints

Any data point associated with a 24-hour recording period (1440 minutes), or for a partial recording period, for DAY TIME with <9.1 hours of data for the day time is considered as a data quality data point deviator.

Day = 15 hours, permit 2 hours charging = 13 hours. 70% of 13 hours = 9.1 hours. Exclude data point if active day+sedentary day = <9.1 hours

Night time Endpoints

Any data point for a 24-hour recording period (1440 minutes), or for a partial recording period, for NIGHT TIME with <4.2 hours of data for the night time is considered as a data quality data point deviator.

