Actigraphy - Day/Night measures of physical activity - exploratory efficacy measures 2 measures for 24-hour recording period: Total Activity Score and Maximum Score														
Time Spent Active							Y							
Non-normalised (Average day time active and average night time active) & normalised (% daytime active; % night time active)				Y	Y		Y				Y	Y		
Over All Time Spent sedentary not lying							Y							
Non-normalised (Average day/night time spent sedentary not lying) & normalised (% daytime sedentary not lying; % night time sedentary not lying)				Y	Y		Y				Y	Y		
Over All Time Spent Lying							Y							
Non-normalised (Average day/night over all time spent lying) & normalised (% daytime lying; % night time lying)				Y	Y		Y				Y	Y		
Over All Time Spent Sedentary							Y							

Endpoint / Parameter/ Display Type	Absolute							Change from Baseline						
	Stats Analysis			Summary		Individual		Stats Analysis			Summary		Individual	
	T	F	L	T	F[1]	F	L	T	F	L	T	F[1]	F	L
Non-normalised (Average day/night over all time spent sedentary) & normalised (% daytime sedentary; % night time sedentary)				Y	Y		Y				Y	Y		
Total Activity Score Day/Night (Total Day time Activity score/hour; Total Night Time Activity score/hour)				Y	Y		Y				Y	Y		
Total Activity Score – 24 hour (derived by adding up the day & night scores)				Y	Y		Y				Y	Y		
Maximum Score –24 Hour (Maximum score of day OR night for each 24-hour recording) And Average of 3 values				Y	Y		Y				Y	Y		
Active Periods (Numbers) normalised / hr				Y	Y		Y							
Active Periods (Duration)				Y	Y		Y				Y	Y		
Relationship between the ALSFRS and actigraphy measures	Y	Y						Y	Y					
Actigraphy - Night Time Rest Endpoints - exploratory efficacy measures														
Number Night Time Movement Episodes/Hr (use average)				Y	Y		Y				Y	Y		
Percent Time Night- time Rest Efficiency (use average)				Y	Y		Y				Y	Y		
Rest Fragmentation Index (use average)				Y	Y		Y				Y	Y		
Average Duration Movement Episodes				Y	Y		Y				Y	Y		

Endpoint / Parameter/ Display Type	Absolute						Change from Baseline							
	Stats Analysis			Summary		Individual		Stats Analysis			Summary		Individual	
	T	F	L	T	F[1]	F	L	T	F	L	T	F[1]	F	L
Data Quality Deviators														
Data Quality Deviators for Actigraphy				Y										
Data Quality Deviators for Heart Rate Variability				Y										
Reconciliation for Actigraphy and Diary Data														
Reconciliation of Actigraphy and Diary Data				Y										

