
Activity classifiers = Active / lying / “sedentary not lying”.
 
NMTMSG – expected to be 24 hr (1440 mins) but could be less if partial recording day NMTMSG = Active, lying, “sedentary not lying”, off
 
Each activity classifier & activity endpoint is recorded by McLaren TWICE, once for day time once for night time.
 
1440 = day time Active, day time lying, day time “sedentary not lying”, day time off + night time Active, night time lying, night time “sedentary not lying”, night time off
 
Therefore, wear time = 1440 minus [day off time + night off time]
 
Off time here represents the time that the sensor was either switched off or the patient was not wearing it (or both).
 
For all the parameters, derivation will be done twice – one with all data and one with the quality data (i.e., excluding data quality deviators).

For each endpoint for the CSR (& interpretation of the study) 3 splits of data will be reported:

- Day time activity endpoints – from McLaren
- Night time activity endpoints – from McLaren
- 24 hour endpoints – derived by GSK – add day time + night time values

DERIVED	Wear time (mins)	Time Active + Time sedentary [where time sedentary = time lying + time sedentary not lying]
DERIVED	Duration of day time wear time (mins)	Day time wear time = day time Active + day time lying + day time “sedentary not lying”
DERIVED	Duration of night time wear time (mins)	Night time wear time = night time Active + night time lying + night time “sedentary not lying”
ACTIVETM	Overall time spent active Average day time active % daytime ACTIVE % night time ACTIVE	Number mins per day/night for 24-hour recording period Add up the total amount of time active across all the recording periods and divide by the number of recording periods. 1 value per subject per time point DAYTIME ACTIVETM (Day 1+2+3) divided by total amount of day time duration across the 3 recording days – expressed as a % Where total amount of daytime duration = [Day 1-day time ACTIVETM + day time LIETM + day time “sedentary not lying” – SEDTMNL] + Day 2 (ditto) + Day 3 [ditto] NIGHTTIME ACTIVETM (Day

		
1+2+3) divide by total amount of night time duration across the 3 recording days – expressed as a %
 
Where total amount of night time duration = [Day 1-night time ACTIVETM + night time LIETM + night time “sedentary not lying” – SEDTMNL] + Day 2 (ditto) + Day 3 [ditto]

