SEDTMNL	
Overall time spent sedentary not lying
 
% daytime SEDENTARY NOT LYING
 
% night time SEDENTARY NOT LYING
	Needs the same approach as above
LIETM	
Overall time spent lying
 
% daytime LYING
 
% night time LYING
	Needs the same approach as above
SEDTM	
Over all time spent sedentary
 
% daytime SEDENTARY
 
% night time SEDENTARY
	Same Approach as above
OFFTM	Time spent with sensor	
ACTIVISC	
Total activity score
 
24- Hour
 
Daytime total activity score
 
Night time total activity score
	
Total Activity Score (add day + night)
 
Day time total activity score (Day 1+2+3) divide by the total day time for that protocol time point.
 
Night time total activity score Day (Day 1+2+3) divide by the total day time for that protocol time point.

MAXACTSC	The maximum score from a 1 min window in a 24-hour	3 values per protocol time point or more if more days are

	
period
 
Daytime maximum activity score
 
Daytime mean maximum activity score (mean of all recording periods)
 
Night time maximum activity score
 
Night time mean maximum activity score (mean of all recording)
	
recorded for home monitoring.
 
 • Take the maximum over the 3 days • Average over 3 days
WKPER01, WKPER02, WKPER05, WKPER15, WKPER30	Active Periods (Numbers)	To normalise 'Active Periods (Number)' to a per hour unit (Algorithm is given below)
WKPERDUR	Average duration of active periods greater than 1 minute.	

To normalise 'Active Periods (Number)' :

1. Add up the total number of 'active periods' for the recording periods (value 1).
 - Please note this is done by adding the 'number of active periods (all the categories) 1min<x<2min' + 'number of active periods 2min<x<5min' + 'number of active periods 5min<x<15min' + 'number of active periods 15min<x<30min' + 'number of active periods >30min'
2. Calculate the 'wear time' for the recording period in days(i.e. minutes/ 1440). (value 2).
 - Please remember that 'wear time = active + sedentary time' for the recording period (either day time or night time)
3. Value 1 / Value 2 is the normalised measure required

Rules for reconciliation of Actigraphy and Diary data

Actigraphy and Diary data will be reconciled and a frequency table on the rules below will be summarized;

Rule1: Subjects present both in Actigraphy and Diary data

Rule2: Subjects present only in Actigraphy data

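### The night-time total activity score is divided by total day time, so it is not the per-hour night score that Table 3 names

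*SAP*

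**What the plan says.** The total activity score (ACTIVISC) row in SAP Section 9.4.3 is the only place where the plan says how the night score is normalised: "Night time total activity score Day (Day 1+2+3) divide by the total day time for that protocol time point". The daytime line directly above it has the same denominator.

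Other parts of the SAP point to a night denominator:

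- Table 3 (Section 7.1.1) lists the endpoint as "Total Night Time Activity score/hour".
- The percentage of night time active is divided by night duration: "Where total amount of night time duration = [Day 1-night time ACTIVETM + night time LIETM", plus night time sedentary not lying. The sedentary and lying rows follow the same approach.
- The Active Periods (Number) algorithm uses wear time "for the recording period (either day time or night time", so the denominator matches the period counted.
- Night wear already exists as a derived variable: "Duration of night time wear time (mins").

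The programming note for Table 2.35 (Section 9.11.4) names a day and a night score but gives no denominator, so it does not settle the matter.

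**The concern.** Section 9.4.3 is the specification a programmer would code from. Coded literally, it scales night movement by time recorded in the day. Daytime sensor wear then enters a measure meant to describe the night.

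The plan itself expects wear to vary. Section 7.1.1 sets minimum-data rules and notes that nights may yield less usable data because of the disease or the technology. If wear changes as patients progress, the endpoint would move even when night movement per hour does not. Less daytime wear would look like more night activity, and less night wear would look like a decline. Either could be taken for a progression signal, or could hide one, when the score is set against ALSFRS-R.

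**Working it through.** **1. Inputs (Section 7.1.1), reproduced.** Day: 15 h less 2 h charging = 13 h; 0.70 × 13 = 9.1 h. Night: 9 h less 2 h charging = 7 h; 0.60 × 7 = 4.2 h = 252 min. Both limits match the plan. There is one charging allowance per 24 hours ("As this study utilises 22 hours recording (2 hours permitted for charging")), so the consistent extremes are charging wholly by day (13 + 9 = 22 h) or wholly by night (15 + 7 = 22 h).

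**2. Error factor.** Let *r* be the true night score per hour, *n* total night wear and *d* total day wear, in hours. The summed night score is *r·n*. Reading total day time as day wear, the written value is *r·n/d*, so

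written / true = *n/d*.

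This reading is an assumption. It is supported by the daytime duration defined for the percentage-active endpoint in Section 9.4.3 (day active + lying + sedentary not lying).

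- Nominal hours: 9/15 = 0.60
- Charging by day: 9/13 = 0.69
- Charging by night: 7/15 = 0.47

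**3. False change with *r* constant (three-day sums).**

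| Change in wear | Charging by day: baseline 27/39 = 0.692 | Charging by night: baseline 21/45 = 0.467 |
|---|---|---|
| One day falls to 9.1 h | 27/35.1 = 0.769, +11% | 21/39.1 = 0.537, +15% |
| All three days fall to 9.1 h | 27/27.3 = 0.989, +43% | 21/27.3 = 0.769, +65% |
| One night falls to 4.2 h | 22.2/39 = 0.569, −18% | 18.2/45 = 0.404, −13% |
| All three nights fall to 4.2 h | 12.6/39 = 0.323, −53% | 12.6/45 = 0.280, −40% |

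The correct change is zero in every cell. These are illustrations, not bounds. They sit at the plan's own data-quality limits, and the all-data outputs have no wear floor. If *n/d* were constant, relative change would be unaffected.

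**4. Separate day and night exclusions.** The SAP states "For all the parameters, derivation will be done twice", once on all data and once on quality data. Assume an excluded period leaves only its own sum, with 13 h days and 9 h nights. Dropping one day but keeping its night gives 27/26 = 1.038 against 0.692, or +50%. Dropping one night but keeping its day gives 18/39 = 0.462, or −33%.

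**5. Other readings of the term.**

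- *Nominal 15 h per day.* Day wear drops out. Night wear does not: 27/45 = 0.600 falls to 12.6/45 = 0.280, still −53%. The dropped-day effect depends on whether the excluded day's 15 h is also removed. If it is, 27/30 against 27/45 is again +50%; if 45 h is kept, there is no change.
- *Total recorded time.* The factor becomes night wear over total wear: 9/24 = 0.375 at nominal hours. With charging by day, 9/22 = 0.409 rises to 9/18.1 = 0.497 when days fall to 9.1 h (+22%), and falls to 4.2/17.2 = 0.244 when nights fall to 4.2 h (−40%).

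No reading gives a score per hour of night wear.

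**6. Secondary unit point.** The Active Periods (Number) algorithm divides by wear in days (minutes/1440), while Table 3 and the endpoint row both describe a per-hour measure. Values are a constant 1440/60 = 24 times the stated unit.

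**The case against.** The case for a lower rating is reasonable. The line reads as a copy of the one above it, and Table 3, the derived night wear and the parallel night endpoints all point to the intended rule. A careful programmer might correct it unprompted. The study has no primary endpoint, and this is one exploratory measure among many. The larger percentages need full wear at one visit and threshold wear on every day or night at another, and the plan gives no wear data to show how common that is.

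The reach is also partly inferred. The Table 2.35 note does not say per hour. Table 3 attaches its normalised and non-normalised labels to the time-spent rows rather than to the activity score. Whether a normalised night score enters the correlations is therefore not stated outright, although Section 7.1.2 calls for both forms of the data.

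These points limit the weight of the finding and leave the contradiction standing. A silent correction would leave reported values that do not follow the documented derivation. The Active Periods unit is a separate labelling defect and adds no weight to the main point.

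**Conclusion.** The rule is wrong as written and should be corrected. It contradicts the endpoint's own label on every reading of the undefined term. The ratios 0.60, 0.69 and 0.47 and the percentages tabulated above rest on the day-wear reading and on a constant true night score.

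The reach is limited:

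- **Affected:** the night part of Tables 2.35–2.41 and Figures 2.17–2.20, so far as they show the per-hour score, and any correlation with total ALSFRS-R that uses the normalised night score.
- **Not affected:** the motor-domain correlations, which take only the 24-hour and day scores.
- **24-hour score:** the rule is "add day time + night time values". It is unaffected if the un-normalised values are added, but the SAP does not say which are.

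The Active Periods discrepancy is a constant factor and alters neither correlations nor relative change.

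**What to change.** In the ACTIVISC row of Section 9.4.3:

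- Divide the summed night score by total night-time wear (night active + lying + sedentary not lying) for that protocol time point, in hours.
- State that the day score is divided by day-time wear in hours.
- Name the conversion from minutes, since wear is derived in minutes.

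Separately, for Active Periods (Number), either divide wear by 60 instead of 1440 or relabel the result as per 24 hours of wear.

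The cost is SAP wording and derivation code. No new data are needed, because night wear is already derived.

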2.2. Study Objective(s) and Endpoint(s)

Objectives	Endpoints
Exploratory Objectives	Exploratory Endpoints

Explore the application of actigraphy:
 
 • For measuring movement/physical activity in ALS subjects • As a marker of ALS disease progression 	
 • Change over time in measurements of movement/physical activity by accelerometer-reported by day and night time. Measurements include Duration of wear time, (combining day & night values to give Wear time), Overall time spent active, Overall time spent sedentary not lying, Overall time spent lying, Overall time spent sedentary, Time spent with Sensor off, Total Activity Score, the maximum score from a 1 min window in a 24-hour period and 5 x Active Periods (5 categories: >1 to <=2min active up to >30mins active) • Change over time in measurements of night time rest by accelerometer reported endpoints: Percent Time Lying Down (at night), Number Night Time Movement Episodes, Number Night Time Movement Episodes/Hr, Percent Time Night-time Rest Efficiency, Rest Fragmentation Index =Move Time/Num Movement Episode, Average Duration Movement Episodes • Relationship between the ALSFRS and accelerometer measures of movement/activity and night time rest endpoints.

Explore the application of continuous remote monitoring of heart rate measures:
 
 • For measuring autonomic nervous system function in ALS subjects • As a marker of ALS disease progression 	
 • Change over time in heart rate variability (HRV) as measured by a heartbeat sensing electrode. Measurements include: 
 ○ Mean and variance for LF/HF (lying, sedentary not lying, active). ○ Mean and variance for HRV effect of being upright = LF/HF sedentary not lying minus LF/HF lying ○ Mean and variance for HRV effect of activity = LF/HF active minus LF/HF lying ○ Mean and variance for RMSSD (24 hours)

Objectives	Endpoints
	
 • Relationship between the ALSFRS and biotelemetry measures of HRV.

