2.55.	FAS	EFF_T1	Summary of Monthly Rate of Decline of Maximum Score (1 min – 24 Hour Window) (Quality data)	Same as above	SAC
2.56.	FAS	EFF_T1	Summary of Active Periods (Numbers) (All data)	For day and night active periods separately & for each category (> 1 to <= 2 minutes, > 2 to <= 5 minutes etc. etc): Categorise into Day and Night Time Modify EFF_T1 as: Add n (%) instead of statistics Add columns for categories	SAC
2.57.	FAS	EFF_T1	Summary of Active Periods (Numbers) (Quality data)	Same as Above	SAC

Efficacy: Tables					
No.	Population	IDSL / TST ID / Example Shell	Title	Programming Notes	Deliverable [Priority]
2.58.	FAS	EFF_T1	Summary of Active Periods (Duration) (All data)	Categorise into Day and Night Time	SAC
2.59.	FAS	EFF_T1	Summary of Active Periods (Duration) (Quality data)	Same as Above	SAC
2.60.	FAS	EFF_T1	Summary of Change from Baseline of Active Periods (Duration) (All Data)	Same as Above	SAC
2.61.	FAS	EFF_T1	Summary of Active Change from Baseline of Periods (Duration) (Quality data)	Same as Above	SAC
2.62.	FAS	EFF_T1	Summary of Relative Rate of Decline of Active Periods (Duration) (All data)	Same as Above	SAC
2.63.	FAS	EFF_T1	Summary of Relative Rate of Decline of Active Periods (Duration) (Quality data)	Same as Above	SAC
2.64.	FAS	EFF_T1	Summary of Monthly Rate of Decline of Active Periods (Duration) (Quality data)	Same as Above	SAC
2.65.	FAS	EFF_T3	Statistical Analysis of Relationship between Absolute Values of Actigraphy endpoints and Absolute Value of Total ALSFRS-R		SAC
2.66.	FAS	EFF_T3	Statistical Analysis of Relationship between Change from Baseline of Actigraphy endpoints and Change from Baseline of Total ALSFRS-R		SAC
2.67.	FAS	EFF_T3	Statistical Analysis of Relationship between Slope of Actigraphy endpoints and Slope of Total ALSFRS-R		SAC

Efficacy: Tables					
No.	Population	IDSL / TST ID / Example Shell	Title	Programming Notes	Deliverable [Priority]
2.68.	FAS	EFF_T3	Statistical Analysis of Relationship between Absolute Values of Actigraphy endpoints and Absolute Value of gross motor domain of ALSFRS-R		SAC
2.69.	FAS	EFF_T3	Statistical Analysis of Relationship between Change from Baseline of Actigraphy endpoints and Change from Baseline of gross motor domain of ALSFRS-R		SAC
2.70.	FAS	EFF_T3	Statistical Analysis of Relationship between Slope of Actigraphy endpoints and Slope of gross motor domain of ALSFRS-R		SAC

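### Active Periods (Numbers) is declared per hour, but its algorithm divides by wear time in days, so normalised values come out 24 times too large; no rate per duration category is defined

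*SAP*

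**What the plan says.** The unit is declared twice. The row for the WKPER variables in SAP Section 9.4.3 gives the purpose as "To normalise 'Active Periods (Number)' to a per hour unit (Algorithm is given below", and Table 3 in Section 7.1.1 lists the endpoint as "Active Periods (Numbers) normalised / hr".

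The algorithm below that row has three steps:

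- Step 1: "Add up the total number of 'active periods' for the recording periods (value 1". The note under it starts from "number of active periods (all the categories) 1min<x<2min" and adds the other four duration categories.
- Step 2: "Calculate the 'wear time' for the recording period in days(i.e. minutes/ 1440). (value 2". Wear time is active plus sedentary time, for either day or night.
- Step 3: "Value 1 / Value 2 is the normalised measure required".

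Elsewhere the endpoint has five parts. Section 2.2 lists "5 x Active Periods (5 categories: >1 to <=2min active up to >30mins active". The programming note for Table 2.56, repeated for Table 2.57, begins "For day and night active periods separately & for each category". The notes for Figures 2.29, 2.30 and 2.32 ask for five day lines and five night lines, one per category.

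**The concern.** Section 9.4.3 is a literal programming instruction. Followed exactly, it produces a number in one unit under a label in another. A reader of the derived-data listings or the time plots would take the values as periods per hour.

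The scale matters because some reported values would be impossible. Every counted period lasts more than one minute, so no subject can have more than 60 in an hour. The algorithm passes 60 as soon as the true rate exceeds 60/24 = 2.5 per hour. If one programmer follows the label and another the formula, outputs for the same endpoint would also differ by a factor of 24.

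The second issue is a gap. The only normalised quantity defined is the pooled rate. Table 3 has a single Active Periods (Numbers) row, the normalised one, while the displays that serve it are laid out by category. The plan does not say what those displays should contain if they are meant to be normalised.

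**Working it through.** **Inputs**

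- Declared unit: per hour (Section 9.4.3, WKPER row; Table 3).
- Divisor as written: wear minutes/1440 (Section 9.4.3, step 2).
- Day wear time for the example: 15 h less 2 h charging = 13 h (Section 7.1.1, daytime data-quality rule). The lower limit for quality data there is 9.1 h.
- Count of 30 periods: assumed, for illustration only.

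**Unit check**

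- As written: count / (minutes/1440).
- As declared: count / (minutes/60).
- Ratio: 1440/60 = 24, independent of count and wear time.

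One day, 13 h = 780 min:

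- As written: 30 / (780/1440) = 30 / 0.5417 = 55.4.
- Per hour: 30 / 13 = 2.31.
- With 33 periods, the algorithm gives 33 / 0.5417 = 60.9, already above the ceiling of 60 per hour.

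Three recording days, 30 periods in total:

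| Day wear | Minutes over 3 days | As written | Per hour | Ratio |
|---|---|---|---|---|
| 9.1 h | 1638 | 26.37 | 1.099 | 24 |
| 13 h | 2340 | 18.46 | 0.769 | 24 |
| 15 h | 2700 | 16.00 | 0.667 | 24 |

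**What the factor reaches**

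- Absolute values, change from baseline and monthly rate of decline are each multiplied by 24.
- Relative rate of decline is (value − baseline)/baseline, so 24 cancels.
- For a correlation, multiplying one variable by 24 multiplies its covariance with the other by 24 and its own standard deviation by 24, so the coefficient is unchanged. A simulated check with 25 pairs gave 0.651 before and after.

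**Category check**

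| Place | Form of the endpoint |
|---|---|
| Section 2.2 | Five categories |
| Section 9.4.3, steps 1 to 3 | One pooled rate, day or night |
| Table 3 | One row, normalised per hour |
| Tables 2.56, 2.57 | By category, counts and percentages, day and night |
| Figures 2.29, 2.30, 2.32 | Five lines by day, five by night |
| Section 7.1.2 | Day-only numbers against gross and fine motor domains, normalised and non-normalised; pooled or by category not stated |

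The five WKPER counts are available for each category, so raw counts can be displayed. No rule gives a rate for each category.

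**The case against.** The best defence is that the unit slip cannot change what the study concludes. Section 9.8 judges endpoints by the strength of the correlation coefficients, and these do not move under a constant factor. Tables 2.56 and 2.57 carry no per-hour label and ask for counts and percentages. Table 3 plans no change-from-baseline display for this endpoint. All of this stands. It limits the damage to the derived listings, the figures and any absolute or change-scale output, but it does not reconcile the label with the formula.

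Pooling can also be defended as an explicit choice: step 1 names every category to be added. That stands too, so pooling is not an arithmetic error. What remains is the mismatch with the five-part endpoint and its displays.

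A reader might infer more: that a subject whose long bouts break into short ones would score as improving, or that the pooled count would hide a marker in the long-bout categories. With assumed bout lengths of 1.5, 3.5, 10, 22 and 40 min, counts of 4/3/2/1/1 give 11 periods and 98.5 active minutes, and counts of 12/8/1/0/0 give 21 periods and 56 active minutes. The count rises 91% while active time falls 43%. The documents do not support the stronger reading. The counts and bout lengths are invented, and the plan never says that a higher count is better. Section 7.1.2 also correlates time spent active and Active Periods (Duration) with the same motor domains. In this example mean bout length falls from 98.5/11 = 9.0 to 56/21 = 2.7 min, so those companion endpoints would show the change.

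Nor does it follow that five category rates must replace the pooled rate in the correlations. Three ALSFRS-R scores in three forms (Tables 2.65 to 2.73) make 9 pairings for one pooled rate and 5 × 9 = 45 for five. Section 9.7.1 acknowledges few subjects, and Section 9.8 makes no multiplicity adjustment.

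**Conclusion.** The unit contradiction is certain and rests on the SAP text alone: the normalised values are 24 times the declared unit for every subject, visit and wear time. The example of 55.4 against 2.31 per hour assumes 30 periods; the ratio assumes nothing.

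Correlation coefficients and relative rate of decline are unaffected. For the mixed model this relies on each response having its own variance, as the unstructured matrices in Section 7.1.2 provide, and on any covariate having a separate coefficient for each response.

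The category point is an inconsistency of specification: a pooled rate is defined, the endpoint and its displays are by category, and the form used in the correlations is left open. Its effect on results cannot be sized from the document.

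This should be fixed before outputs are programmed. It is not critical, because it touches one exploratory endpoint in a study without a primary endpoint.

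**What to change.** 1. In step 2 of the algorithm, define value 2 as wear minutes/60. The alternative is to keep the divisor of 1440 and relabel the endpoint as per 24 hours of wear in the WKPER row, Table 3 and every output. Hours are easier to read: a day-only rate per 24 hours of wear can be mistaken for a count per calendar day.
2. Add a rule for each WKPER category: category count divided by the matching day or night wear hours. Use it for Figures 2.29, 2.30 and 2.32, and for Tables 2.56 and 2.57. State in the table notes how it sits with the counts and percentages now requested.
3. Keep the pooled rate as specified.
4. State in Section 7.1.2 whether the pooled rate, the category rates or both enter the day-only correlations. If category rates are added, acknowledge the larger number of pairings.

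The cost is SAP wording and programming, with no new data. Item 4 adds correlation output only if category rates are chosen.
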